As shown in Figure 1, cumulative alcohol dosing procedures generate highly reproducible BALs and subjective effects, with little between-subject variability. Subjective effects track BAL across the ascending and descending limb of the curve. Using this procedure, we have shown that the GABRA2 gene influenced alcohol subjective and physiological effects (Uhart et al., 2013). To date, we have completed this procedure over 150 subjects.

[figure not shown]

Figure 1. Time course of BAL and self-rated effects on the VAS and SHAS. Arrows indicate times of placebo

(P) and each alcohol drink (A1, A2, A3) consumed.

Discharge and Follow-up:

AUD subjects are discharged on day 7 following cognitive assessment and participation in a brief motivational intervention for alcohol use; information on treatment availability will be provided prior to discharge from the CRU. Under the supervision of [name], the intervention is delivered by Master's-level staff following procedures outlined in NIAAA Clinician Guide to Brief Intervention.

All female participants are advised to use nonhormonal birth control (e.g., condoms) for the duration of a one month period following discharge. All male participants will also be advised to use condoms for the duration of the follow-up visits and for at least 5 half-lives of the drug plus 90-days after the last dose of mifepristone. All subjects will be given a supply of condoms.

AUD subjects return weekly for 2 follow-up visits. HC subjects return one week post-second fMRI for a follow-up visit. As described above, MIFE is a long acting compound; plasma levels will likely remain elevated throughout the first two weeks post-discharge at the time of the follow-up visits. At each follow-up visit, participants provide self-reported alcohol use using TLFB procedures for the period since they were last seen, complete self-report measures of alcohol craving (as listed under the inpatient stay), medication side effects (SAFTEE) and adverse events. In addition, we will obtain a blood spot for PEth determination as a biomarker of recent drinking intensity. We also will get a blood sample for MIFE level and, at week 1 follow-up, a sample will be obtained to test for potassium level. Subjects will be reminded of the importance of use of nonhormonal birth control and/or condoms and will be provided with condoms.

b. Study duration and number of study visits required of research participants.

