Each subject will participate in an initial assessment, and a possible second assessment visit for completion of medical history, vital signs and laboratory tests. AUD participants will be admitted to the CRU for 6 nights. HC participants, who participate in the study on an outpatient basis, will continue MIFE dosing and salivary sample collection at home. For AUD participants, there are two follow-up visits at 1 and 2 weeks following CRU discharge. For HC participants, there is one follow-up visit at 1 week following the second fMRI. It is anticipated that subjects will complete all study procedures within a 6 month period.

c. Blinding, including justification for blinding or not blinding the trial, if applicable.

Staff and subjects will be blind to the alcohol and MIFE doses administered during this study to reduce expectancy effects.

d. Justification of why participants will not receive routine care or will have current therapy stopped.

Subjects are not seeking treatment for their AUD; they will not currently be engaged in therapy.

e. Justification for inclusion of a placebo or non-treatment group.

A placebo MIFE dose is included for comparison with the active drug effects and to control for expectancy effects.

f. Definition of treatment failure or participant removal criteria.

A participant will be removed from the study if s/he experiences a moderate or severe adverse event, is noncompliant with study or CRU rules, or if it is determined by the study physician to be unsafe to continue.

g. Description of what happens to participants receiving therapy when study ends or if a participant's participation in the study ends prematurely.

MIFE dosing is discontinued at the time of discharge from the study.

5. Inclusion/Exclusion Criteria

Healthy, non-treatment seeking, 21-60 years old, male and female subjects will be recruited through the media. Recruitment uses a mix of newspaper, radio, and on-line advertisements. Based on the 2011 census, the Baltimore metropolitan area is mostly Caucasian (61%) or African-American (30%); the remaining 9% is Asian (4%) and persons reporting two or more races (5%); 8.8% of the population report Hispanic ethnicity.

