This study will include two groups of participants – persons with AUD and healthy controls. AUD subjects will have a current DSM 5 alcohol use disorder and will be actively drinking at least 50% above NIAAA recommended guidelines (women >10 drinks/week and men >20 drinks/week) and at least 5 binge drinking episodes in the past 30 days. Recent heavy drinking will be confirmed by PEth blood spot analysis ≥ 50 ng/mL. HC subjects will not meet DSM 5 criteria for AUD and will not be drinking above NIAAA recommended guidelines as confirmed by PEth blood spot analysis < 50 ng/mL. We expect to consent 450 subjects in order to accrue 150 subjects into the study procedures (N=75 for AUD and N=75 healthy controls). Historically, our retention in the CRU has been outstanding, with over 90% of subjects completing the protocol.

Additional Inclusion Criteria for all subjects:

- Nontreatment seeking volunteers;
- 21 – 60 years old;
- English speaking;
- 5th grade literacy to ensure ability to read study assessment instruments;
- no current serious psychiatric or health problems that would contraindicate study participation;
- BMI > 19 and < 40 ; medication dosing is not weight-adjusted. We have restricted the weight range of participants to reduce weight-associated variability;
- For women, negative urine pregnancy test prior to initiating MIFE treatment and agreement to use nonhormonal birth control for 2 weeks following last MIFE dose. A medical record of surgical sterilization or elevated FSH level confirming post-menopausal status is required to document non-childbearing potential;
- No adult seizure history;
- No serious alcohol withdrawal complications in prior alcohol withdrawal episodes;

- Some non-drinking days on 90-day TimeLine Followback Drinking Calendar;
- Study Physician and PI recommendation.

Exclusion criteria for all subjects:

- Women on hormonal birth control, or who are pregnant, nursing or planning pregnancy; women with unexplained vaginal bleeding;
- Current DSM 5 mood, anxiety or psychosis diagnosis or currently treated with psychiatric medication;
- Current substance use disorder except alcohol, marijuana (mild) or tobacco; current illicit drug use other than marijuana;
- History of serious alcohol withdrawal symptoms (e.g., seizures, hallucinations) or history of inpatient, medicated alcohol withdrawal management, and CIWA-Ar score at time of assessment ≥ 12 ;

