Mifepristone (MIFE) Administration: Since MIFE blocks the progesterone receptor, treatment of a pregnant woman would result in the termination of pregnancy. All females must have a negative urine pregnancy test prior to MIFE initiation; women on hormonal birth control, who are pregnant, nursing or planning pregnancy, and women with unexplained vaginal bleeding are excluded from study participation. In addition, women must agree to use a non-hormonal form of birth control for at least 1 month after stopping MIFE treatment. We will provide female participants with condoms at each outpatient follow-up visit. Women may experience endometrial thickening or unexpected vaginal bleeding; there is a low likelihood of these events.

Due to the anti-progestin effects of mifepristone and given the lack of adequate data on the potential levels of mifepristone in semen, male subjects will be required to employ barrier protection with their female partners. Males should use barrier protection during intercourse for at least 5 half-lives of the drug (half life = 18 hours) plus 90-days (the duration of one spermatogenic cycle in men and residence time for unejaculated sperm) after last dose of mifepristone to avoid risk of anti-progestin effects transmitted to female sexual partners. We will provide male participants with condoms for at least 94-days after the last dose of mifepristone.

Based on prescribing information for MIFE treatment of Cushing Disease, MIFE may produce prolongation of the QT interval of the electrocardiogram (ECG) and use of MIFE with QT interval-prolonging drugs is contraindicated. A recent evaluation of the cardiac safety of three doses of 1200 mg MIFE given every 12 hrs to subjects found no clinically meaningful QT prolongation in healthy subjects (Corcept Therapeutics Investigator Brochure).

Based on data in individuals with Cushing Disease, MIFE may cause adrenal insufficiency. Symptoms of adrenal insufficiency may include abdominal pain, vomiting, muscle weakness and fatigue, depression, extremely low blood pressure (hypotension), weight loss, changes in mood, and shock (adrenal crisis). There has been no evidence of the development of adrenal insufficiency during short-term administration of MIFE doses up to 1200 mg in clinical trials for other psychiatric disorders.

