Mifepristone administration: The use of MIFE in this study will be under FDA IND 124365; [name], Co-Principal Investigator, holds the IND. We are taking multiple precautions to ensure that MIFE is not administered to women who are pregnant or planning pregnancy. Alcohol is highly toxic and pose significant risk to fetal development. We believe it is imperative to study therapeutic agents in women of childbearing age to further the development of potential treatments for this population.

- Only persons with no medical exclusions will be enrolled for study participation.
- Subjects are under continuous observation while on the Clinical Research Unit. Subjects not on the CRU are checked on daily while receiving MIFE.
- Medication side effects and adverse effects are formally monitored daily on the CRU for inpatient subjects, on the phone for outpatient subjects, and during outpatient visits via the SAFTEE. In case of an emerging or adverse event, the study physician is available by cell phone for assistance.
- Women who use hormonal birth control, are pregnant, planning to become pregnant or are nursing are excluded from study participation. All females must have a negative urine pregnancy test prior to MIFE initiation. Females must use a non-hormonal medically acceptable method of contraception (e.g., condoms, IUD, diaphragm) for a one month period following discharge, unless the subject has had a surgical sterilization. We will provide female participants with condoms for the month following study participation. Women who provide a report of surgical sterilization or

- who provide a lab report with FSH level greater than 25 confirming post-menopausal status may be exempt from pregnancy testing.
- Due to the anti-progestin effects of mifepristone and given the lack of adequate data on the potential levels of mifepristone in semen, male subjects will be required to employ barrier protection with their female partners. Males will be instructed to use barrier protection during intercourse for at least 5 half-lives of the drug plus 90-days (the spermatogenic cycle in men and residence time for unejaculated sperm) after last dose of mifepristone to avoid risk of anti-progestin effects transmitted to female sexual partners.
- Women who develop unexplained vaginal bleeding during the study will be excluded for further study procedures. Female study subjects will be educated to report and be evaluated for unexplained vaginal bleeding.

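### Eligibility accepts a 2-week contraception agreement from women, while the risk section requires at least 1 month

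*Combined protocol and SAP*

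**What the plan says.** Four places in the combined protocol and SAP set the contraception period for women:

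- Section 5, inclusion criteria for all subjects: "agreement to use nonhormonal birth control for 2 weeks following last MIFE dose".
- Section 8a, Mifepristone (MIFE) Administration: "women must agree to use a non-hormonal form of birth control for at least 1 month after stopping MIFE treatment".
- Section 8b, Mifepristone administration: "Females must use a non-hormonal medically acceptable method of contraception (e.g., condoms, IUD, diaphragm) for a one month period following discharge". The same bullet exempts women who have been surgically sterilized and adds "We will provide female participants with condoms for the month following study participation".
- Section 4a, Discharge and Follow-up: "All female participants are advised to use nonhormonal birth control (e.g., condoms) for the duration of a one month period following discharge".

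For men, section 8a states: "Males should use barrier protection during intercourse for at least 5 half-lives of the drug (half life = 18 hours) plus 90-days". It then sets the condom supply at a minimum of 94 days after the last dose. Section 4a (Discharge and Follow-up) and section 8b repeat the rule without a half-life or a day count. Section 4a (MIFE Administration) gives the half-life as 40 hours after a single dose and 84.6 hours after multiple doses.

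**The concern.** The section 5 and section 8a statements are the same kind of requirement, an agreement the woman must give, and both run from the end of dosing. Neither a different starting point nor a distinction between advice and obligation can reconcile them. Staff use the inclusion list to decide who may be dosed, so the shortest period sits where that decision is made.

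The protocol treats contraception as a safety condition. Section 8a opens its discussion by warning that "treatment of a pregnant woman would result in the termination of pregnancy", and in the same paragraph lists the contraception agreement among the safeguards. Followed as written, section 5 admits women who do not meet section 8a.

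The men's item has a different cause. Two sections give different half-lives for the same drug, so the day count depends on which section is read.

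**Working it through.** **Women: comparing the four statements**

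| Place | Period | Starts from | Force |
|---|---|---|---|
| Section 5 | 2 weeks | last dose | must agree, to be eligible |
| Section 8a | at least 1 month | stopping MIFE | must agree |
| Section 8b | 1 month | discharge | must use |
| Section 4a, Discharge and Follow-up | 1 month | discharge | advised |

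Three of the four say one month. No text explains the 2 weeks or says which section prevails.

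Shortfall = one month − 14 days:

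- 30-day month: 30 − 14 = 16 days.
- 28-day month: 28 − 14 = 14 days.
- 31-day month: 31 − 14 = 17 days.

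The different starting points do not account for this. Section 4g says "MIFE dosing is discontinued at the time of discharge from the study". In Table 1, AUD subjects take their last dose on day 6 and are discharged on day 7, a difference of one day. HC subjects have no CRU discharge; if their end of dosing on day 4 is taken as discharge from the study, the difference is about nil.

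**Women: 2 weeks against the protocol's own exposure statements**

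- Section 4a (MIFE Administration) says plasma levels can be detected for up to 2 weeks after stopping.
- Section 4a (Discharge and Follow-up) expects levels to stay raised through the first two weeks after discharge.
- For an AUD woman, the section 5 period ends on day 6 + 14 = day 20. The two weeks after discharge end on day 7 + 14 = day 21. The criterion therefore leaves no margin.
- For illustration, assuming simple first-order elimination at 84.6 h: 14 days is 14 × 24 / 84.6 = 3.97 half-lives, leaving 0.5^3.97, about 6.4%. Thirty days is 30 × 24 / 84.6 = 8.51 half-lives, leaving about 0.3%. At 40 h, 14 days is 8.4 half-lives, again leaving about 0.3%.

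**Men: reproducing the 94 days**

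Days = 5 × half-life (h) / 24 + 90, rounded up.

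| Half-life | Source | 5 half-lives | Plus 90 | Rounded up | Against 94 |
|---|---|---|---|---|---|
| 18 h | section 8a | 3.75 d | 93.75 d | 94 d | matches |
| 40 h | section 4a, single dose | 8.33 d | 98.33 d | 99 d | +5 d |
| 84.6 h | section 4a, multiple doses | 17.625 d | 107.625 d | 108 d | +14 d |

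The 94 days is correct arithmetic from its own input; it is the 18-hour input that conflicts with section 4a. HC subjects take 4 doses (days 1 to 4) and AUD subjects 6 (days 1 to 6). The documents do not say which half-life applies after so few doses, so 108 days is conditional.

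**The case against.** The strongest reply is that the requirements can be met together. A woman who agrees to one month also satisfies section 5, and section 8a's agreement is itself a condition, so read as a whole the stricter term governs. That is how a careful site would probably act, but no passage says so, and the inclusion list is the text most likely to be used alone.

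A second reply is that the pregnancy-termination sentence concerns dosing a woman who is already pregnant. The protocol guards against that with a negative pregnancy test before the first dose and by excluding women who are pregnant or planning pregnancy. This is fair: the period after dosing deals with residual exposure, a narrower risk. Even so, section 8a places the contraception agreement alongside those guards.

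Third, 2 weeks matches the stated limit of plasma detection, so the disputed days, roughly 15 to 30 after the last dose, carry little documented exposure. This also has force: no material hazard over those days has been shown. What remains is that 2 weeks leaves no margin and contradicts the protocol's own requirement.

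Fourth, discharge advice and condom supply already run to one month, with reminders at follow-up visits. This limits the practical harm but does not correct the criterion. HC women have a single follow-up visit, on day 11, and none scheduled later.

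Finally, the consent form was not available, so what women are actually asked to agree to cannot be seen. For men, 94 days is stated as a minimum and is mostly the fixed 90 days. Both points stand, and the men's item adds no weight to the women's.

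**Conclusion.** The concern holds. Section 5 sets a contraception agreement for women that is 16 days shorter than section 8a requires, taking a month as 30 days (14 to 17 days across calendar months). This rests on a direct comparison of the text and on no pharmacokinetic assumption. It should be fixed because it is a safety-related eligibility rule, though the likely harm is small. Nothing in the statistical analysis depends on it.

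The men's point is minor. The stated minimum is 5 days short if the single-dose half-life in section 4a applies, and 14 days short if the multiple-dose value does. If 18 hours can be justified, the 94 days stands.

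**What to change.** **Women.** Change the section 5 bullet to at least 1 month following the last MIFE dose. This is an edit to one bullet. Counting from the last dose in sections 4a, 8a and 8b as well would be tidier, but it is optional because the difference is about 0 to 1 day.

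**Men.** Reconcile section 8a with section 4a (MIFE Administration). Either restate the minimum period and condom supply from a section 4a half-life (99 days at 40 h, or 108 days if the multiple-dose value is adopted for 4 to 6 doses), or justify 18 hours. Then give the resulting day count in section 4a (Discharge and Follow-up), section 8a and section 8b. The cost is one half-life or one sentence of justification, a day count in three places, and at most 14 more days of condoms per man.

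**Consent form.** Check it for the same figures and align it.

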Subjects will be carefully screened and fully informed of study procedures and risks prior to participation in any study procedures. This study involves several procedures, each of which entails some risk of discomfort or side-effects. It also employs several drugs, each of which entails some risk. These risks are discussed by procedure and medication. Participants will receive a thorough description of all potential risks in the consent form.

Assessment procedures: The major disadvantage is the time taken to complete study instruments and questionnaires. Our experience with these evaluations indicates they are acceptable to participants. This study involves questions about dangerous or illegal behavior, psychiatric history, a medical history, and laboratory tests. There is a small risk that participants will become upset during the assessment interview. There also is a risk of breach of confidentiality if the responses were to be disclosed.

Blood draws and urine collection: We will collect blood for health assessment and medication levels. Blood chemistries and urinalysis are performed at baseline, at the time of admission to the CRU (or day 1 for HC participants completing the study on an outpatient basis), and on protocol days 4 – 6. Urinalysis for drug toxicology assessment is performed to identify illicit drug use. A blood spot for PEth testing is obtained for detection of recent heavy drinking; PEth blood spot is collected at assessment and each follow-up visit. Urine pregnancy tests are completed in female subjects at screening and on day 1. A urine pregnancy test is obtained prior to the initial MIFE dose. Blood draw procedures involve minimal risks such a slight risk of discomfort at the intravenous site. A small amount of bleeding under the skin will produce a bruise in about 5% of cases. The risk of temporary clotting of the vein is about 1%. The risk of infection or significant blood loss is less than 1 in 1000. In rare cases, fainting could occur.

Alcohol Withdrawal: Applicants with a history of prior inpatient medicated withdrawal, alcohol withdrawal-related seizures, or other serious alcohol withdrawal symptoms will be excluded from participation. Eligible participants will undergo monitored alcohol abstinence and medically supervised alcohol withdrawal on the CRU.

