Medically supervised and alcohol withdrawal and monitored abstinence: Subjects will be closely monitored by nursing and physician staff for alcohol withdrawal signs and symptoms. All AUD subjects will receive iv administration of 1 liter of normal saline with vitamins over the first 12 hours following admission. On days 1 – 4, the Clinical Institute Withdrawal Assessment - Alcohol Revised (CIWA-Ar), which includes 10-items (nausea/vomiting, tremor, paroxysmal sweats, anxiety, agitation, tactile disturbances, auditory disturbances and visual disturbances), will be completed by CRU nurses every 4 hours while the participant is awake. This well-validated clinical tool will assess alcohol withdrawal symptom severity and is the gold standard to guide benzodiazepine (BZ) administration during symptom-driven withdrawal management (Saitz et al., 1994). If the CIWA score is ≥ 12 the subject is given diazepam (5mg). The CIWA score is repeated 1 hour after each dose. If the score remains ≥ 10 then another diazepam dose (5mg) is given up to a maximum of three doses. Based on our previous study, we anticipate that few subjects will require BZ treatment since we exclude subjects who report a history of withdrawal complications. If systolic blood pressure increases above 180 and/or diastolic blood pressure increases above 105, we may administer atenolol. The most common symptoms of atenolol include dizziness, lightheadedness, tiredness, drowsiness, depression, nausea and diarrhea. Less common but more serious side-effects include: shortness of breath, and swelling of the hands, feet, ankles or lower legs. Subjects who experience seizure activity or delirium tremens will be discontinued from the study; also subjects will be discontinued on recommendation by the study physician. To date we have successfully withdrawn over 98% of our alcohol-dependent subjects without medications requiring protocol termination. Exclusion of subjects with a history of alcohol withdrawal complications, and/or high CIWA scores at assessment is a successful strategy to help ensure subject safety. In the event of a severe reaction or medical emergency, the participant will be transported to near-by emergency services.

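### As worded, the alcohol withdrawal exclusion in Section 5 leaves eligible two groups that Sections 8a and 8b describe as excluded

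*Combined protocol and SAP*

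**What the plan says.** The exclusion list in Section 5 has one bullet on withdrawal risk. It begins with a history of serious withdrawal symptoms, giving seizures and hallucinations as examples, and goes on "or history of inpatient, medicated alcohol withdrawal management, and CIWA-Ar score at time of assessment ≥ 12". This is the only CIWA-Ar criterion in Section 5.

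The inclusion list in the same section has three related items: "No adult seizure history", "No serious alcohol withdrawal complications in prior alcohol withdrawal episodes" and "Study Physician and PI recommendation".

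Two places in Section 8 describe who is kept out:

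- Section 8a, under Alcohol Withdrawal: "Applicants with a history of prior inpatient medicated withdrawal, alcohol withdrawal-related seizures, or other serious alcohol withdrawal symptoms will be excluded from participation". There is no CIWA-Ar condition.
- Section 8b, under medically supervised withdrawal: "Exclusion of subjects with a history of alcohol withdrawal complications, and/or high CIWA scores at assessment is a successful strategy to help ensure subject safety". No cut-off is given for a high score; the figure of 12 comes from Section 5.

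Section 4a, under Alcohol Withdrawal Management, uses the same value of 12 as the on-study trigger for intravenous diazepam or lorazepam.

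**The concern.** The bullet joins its first two items with an or, then attaches the CIWA-Ar score with an and. Taken at its word, an applicant must have a qualifying history and also score at least 12 at assessment before the bullet applies. Section 8a treats prior inpatient medicated withdrawal as sufficient by itself. Section 8b treats a high score as sufficient by itself. If the literal wording governs, Section 5 delivers neither exclusion.

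Section 5 decides who enters a study in which AUD subjects go through supervised withdrawal. An applicant who scores 12 or more at assessment is already at the level at which the protocol would give a benzodiazepine on the unit. The Day 1 checks that General CRU procedures lists before any study procedure do not include a repeat CIWA-Ar. Two screeners following Section 5 could also reach opposite decisions on the same applicant. CIWA-Ar is a secondary outcome in Section 7b and a main outcome for Aim 2 in Section 7c, so the rule also affects who contributes withdrawal data.

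**Working it through.** The plan gives no figure to reproduce here; the check is one of logic.

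**Inputs.** Three yes/no facts describe an applicant:

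- S: history of serious withdrawal symptoms. This is taken to be the same thing as the serious complications barred by the inclusion list.
- M: prior inpatient medicated withdrawal management.
- C: CIWA-Ar of 12 or more at assessment.

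**Rules compared.**

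- Conjunctive reading A: the bullet excludes if (S or M) and C.
- Conjunctive reading B: the bullet excludes if S or (M and C).
- List reading: the bullet excludes if S or M or C.
- Inclusion list: excludes if S, whatever M and C are.
- Section 8a: excludes if S or M.
- Section 8b: excludes if S or C.

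The Section 5 columns below combine the bullet with the inclusion list.

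| S | M | C | Section 5, reading A | Section 5, reading B | Section 5, list reading | Section 8a | Section 8b |
|---|---|---|---|---|---|---|---|
| 0 | 0 | 0 | eligible | eligible | eligible | – | – |
| 0 | 0 | 1 | **eligible** | **eligible** | excluded | – | excluded |
| 0 | 1 | 0 | **eligible** | **eligible** | excluded | excluded | – |
| 0 | 1 | 1 | excluded | excluded | excluded | excluded | excluded |
| 1 | 0 | 0 | excluded | excluded | excluded | excluded | excluded |
| 1 | 0 | 1 | excluded | excluded | excluded | excluded | excluded |
| 1 | 1 | 0 | excluded | excluded | excluded | excluded | excluded |
| 1 | 1 | 1 | excluded | excluded | excluded | excluded | excluded |

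**Result.**

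- Either conjunctive reading: 4 profiles excluded through S, plus 1 (M and C without S), gives 5 of 8.
- List reading, or three separate criteria: 8 − 1 = 7 of 8. Only the profile with none of the three facts stays eligible.
- Difference: 7 − 5 = 2 profiles. These are M alone, which Section 8a excludes, and C alone, which Section 8b excludes.

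Where the brackets go in the conjunctive reading makes no difference once the inclusion list is applied. Apart from the discretionary recommendation by the study physician and PI, nothing else in Section 5 closes either gap.

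**The case against.** The strongest reply is that the list reading is the natural one. The protocol elsewhere uses a comma and an and to list alternatives: Section 8a runs several groups of women together this way when it says they are excluded, and the CYP3A bullet in Section 5 does so for drugs. The conjunctive reading also leaves the bullet with almost no work. The inclusion list already accounts for 4 of the 5 excluded profiles, so the bullet would add only one, and its clause on serious symptoms would exclude nobody new. Sections 8a and 8b then make the intention plain.

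A second reply is that neither group goes unprotected. Entry needs the physician's and PI's recommendation. Section 4a provides CIWA-Ar every 4 hours while awake, benzodiazepine at 12 or more, and transfer and termination if scores stay at 10 or more after repeat dosing. Section 8b reports that over 98% of earlier subjects were withdrawn without medication that required termination.

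Much of this stands. Three separate exclusions are very probably what was meant, the comma permits that reading, and on-unit monitoring limits the consequences. The count of 5 against 7 is of logical profiles, not people.

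It does not remove the problem. The parallels are a list of persons and a list of drugs; neither changes connector partway, as this bullet does. A screener works from the eligibility list and should not need the risk section to decode it. Discretion states no rule, and monitoring after admission does not correct who is admitted. The 98% figure is presented alongside the exclusion strategy that the literal wording fails to deliver, so it cannot vouch for applicants whom that strategy would have kept out.

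**Conclusion.** The concern holds. The bullet is wrong as written: followed literally, Section 5 admits two groups that the protocol elsewhere describes as excluded, and on the alternative reading it is still ambiguous.

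The history gap is narrow. It covers prior inpatient medicated withdrawal without serious complications, because adult seizures and serious complications are barred on any reading. The CIWA-Ar gap covers anyone scoring 12 or more without a qualifying history.

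The conclusion rests on two assumptions: that serious symptoms in the exclusion bullet and serious complications in the inclusion list mean the same thing, and that a high score in Section 8b means the Section 5 value of 12. How many applicants fall in either group cannot be worked out from the documents. The point concerns screening consistency and subject safety; it does not touch randomisation, the analysis models, power or sample size. It should be corrected.

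**What to change.** Replace the bullet with three stand-alone exclusions, any one of which is sufficient:

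1. A history of serious alcohol withdrawal symptoms, with the present examples kept.
2. A history of inpatient medicated management of alcohol withdrawal.
3. A CIWA-Ar score of 12 or more at assessment.

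Section 5 then agrees with Sections 8a and 8b, and only applicants with none of the three facts pass this part of screening. The cost is a one-line protocol correction. No assessment, visit or analysis is added.
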